| CAR | Center for Autism Research |
| CHOP | The Children's Hospital of Philadelphia |
| C-JARS | Childhood Joint Attention Rating Scale |
| DAS-II | Differential Ability Scales, 2 nd Edition |
| EOWPVT | Expressive One-Word Picture Vocabulary Test, 4 th Edition |
| GLM | General Linear Model |
| IRB | Institutional Review Board |
| PI | Principal Investigator |
| PPVT | Peabody Picture Vocabulary Test, 4 th Edition |
| SRS | Social Responsiveness Scale |
| Subject Computer Setup | Laptop computer with integrated use of a consumer grade eye tracker connected to it via a USB connection |
| SAE | Serious Adverse Event |
| TDC | Typically Developing Children |
| TOVA | Test of Variables of Attention |

ABSTRACT

Background:

Autism spectrum disorder (ASD) is a neurodevelopmental disorder characterized in part by difficulty in social interaction and communication [1], which can affect individuals' employability, educational achievement, and quality of interpersonal relationships [2-4]. Existing therapies targeting the deficits of the school-age population with ASD require significant therapist or educator time and are thus very costly, with estimates of the economic impact of caring for children with ASD ranging from ~\$12B [5] to \$61B annually [6]. Given this, as well as the fact that ASD affects 1 in 59 children in the United States [7], with identified prevalence rising [5], there is a pressing need for cost-effective, evidence-based interventions to support the ASD community, and BioStream Technologies, LLC (BioStream), in collaboration with the Center for Autism Research (CAR) at the Children's Hospital of Philadelphia (CHOP), has developed one such intervention: the BioStream Computer-Based Social Skills Training (BioStream Training). The intervention to be used in this protocol has been piloted at CHOP as part of an existing IRB protocol (eIRB #15-12594). As part of that protocol, we have run 32 children (18 with ASD and 14 TDC) through procedures that to some degree are overlapping with the present protocol (up to 5 study sessions of gameplay per subject).

Primary and Secondary Aims:

The objective of this study is to evaluate changes in subject performance on social skills assessments after engaging in BioStream Training, as compared to a group of subjects who were trained with an alternate control game, and to evaluate possible correlations in changes in social skills assessments with changes in subject gameplay performance.

Study Design:

This is a comparison group study during which subjects will engage with BioStream Training in a home, school, therapy center, or research organization setting and participate in social skills assessments, or will be exposed to an alternate computer video game in a home, school, therapy center, or research organization setting instead of the BioStream Training.

Setting/Participants:

All participants will participate in the study either in a home, school, therapy center, or research organization setting. The study will involve 150 subjects aged 4-14 with ASD.

Study Interventions and Measures:

BioStream Training is computer-based social skills training that includes interactive game-like applications involving images, video, audio, and animation (e.g. animated characters). The main study outcome measures include both standard and experimental social skills assessments (e.g. a dyadic interaction task with a member of the study team).

PROTOCOL SYNOPSIS

| | |
|---|--|
| Study Title | Computer-based social skills training for autism spectrum disorder |
| Funder | BioStream Technologies, LLC |
| Clinical Phase | N/A |
| Study Rationale | 
Autism spectrum disorder (ASD) is a neurodevelopmental disorder characterized in part by difficulty in social interaction and communication, which can affect individuals' employability, educational achievement, and quality of interpersonal relationships. Existing therapies targeting the deficits of the school-age population with ASD require significant therapist or educator time and are thus very costly. Given this, as well as the fact that ASD affects 1 in 59 children in the United States according to the Center for Disease Control, there is a pressing need for cost-effective, evidence-based interventions to support the ASD community, and BioStream Technologies, LLC (BioStream), in collaboration with the Center for Autism Research (CAR) at the Children's Hospital of Philadelphia (CHOP), has developed one such intervention: the BioStream Computer-Based Social Skills Training (BioStream Training).
 |
| Study Objective(s) | 
Primary
 
To evaluate changes in subject performance on various social skills assessments (including eye-tracking, dyadic interaction, SRS, Ekman 60 Faces Test) after engaging in BioStream Training, including in comparison to an alternate game.
 
Secondary
 
To observe changes in subject gaze patterns during social skills assessments after engaging in BioStream Training, including in comparison to an alternate game.
 
To observe possible correlations in changes in social skills assessments with changes in subject gameplay performance.
 |
| Test Article(s) (If Applicable) | BioStream Training is computer-based social skills training that includes interactive game-like applications involving images, video, audio, and animation (e.g. animated characters). |
| Study Design | Comparison Group |
| Subject Population key criteria for Inclusion and Exclusion: | 
Inclusion Criteria
 
 1. Ages 4-14. 2. Meets diagnostic criteria for ASD. 3. Estimated intelligence standard score of at least 40 (can be substituted for a receptive language score such as PPVT or use |

of the Differential Ability Scales, 2nd Edition (DAS-II)).

4. Parent reports difficulty with at least one of two social skills (via modified questions from the Social Responsiveness Scale)
5. English as the child's primary/first language (key measures used in the study do not have alternate language versions).
6. Attains a score equal to or less than 75% correct on the Ekman 60 Faces Test.
7. The parent who completes the questionnaires needs to be proficient in English.
8. Has successfully played a video game using a Microsoft Xbox game controller, Sony PlayStation game controller, or other comparable game controller.
9. Parental/guardian permission (informed consent) and if appropriate, child assent.
10. Wi-Fi internet connection at subject's home/school/therapy center/research organization available for use by study laptop computer.

Exclusion Criteria

1. History of seizures.
 2. History of traumatic brain injury or other significant medical or neurological abnormality affecting motor or higher cortical functioning.
 3. Certain visual, auditory, DSM 5, or conduct disorders (see below).
 4. A visual disorder that cannot be corrected through the use of corrective lenses to a level of 20-40 in both eyes.
 5. Use of corrective visual lenses that would significantly impede the valid collection of visual attention and gaze pattern data during dyadic interaction tasks.
 6. Auditory impairment (that cannot be corrected by a hearing aid) that would significantly impede the valid collection of test measures.
 7. Profound intellectual disability or sensory-motor difficulties that would preclude valid use of diagnostic instruments and/or use of a computer or mobile computing device.
 8. A DSM 5 disorder or other psychiatric symptoms that would interfere with the participant's ability to participate in the study (e.g., active psychosis), per parent report.
 9. History of one or more psychiatric hospitalizations.
 10. Presence of significant symptoms of a conduct disorder.
-

| | |
|---------------------------|--|
| Number Of Subjects | 150 subjects with subject participation at home, school, therapy center, or research organization. |
| Study Duration | 
The study is comprised of two phases. For Phase I, each subject's participation in BioStream Training or the alternate game will last for up to 6.67 to 33.33 hours over a 28-day period (up to 20 game play sessions, up to 5 days per week for between 20 minutes and 100 minutes per training session or alternate game session) plus approximately 8 hours of assessment and other study related activities. Each parent's participation will last for approximately 4.25 total hours over the 28 day period excluding time spent for oversight of the subject during the BioStream Training or during play of the alternate game.
 
For Phase II, each subject's participation in BioStream Training or the alternate game will last for up to 6.67 to 33.33 hours over a 28 day period (up to 20 game play sessions, up to 5 days per week for between 20 minutes and 100 minutes per training session or alternate game session) plus about 5 hours of assessment and other study related activities. Each parent's participation will last for about 2.5 total hours over the 28 day period excluding time spent for oversight of the subject during the BioStream Training or during play of the alternate game. It is not required that Phase II begin immediately upon completion of Phase I.
 |
| Study Phases | 
Phase I
 
 • Initial Screening • Visit 1 – Informed Consent, Ekman 60 Faces Test, PPVT • Visit 2 – Assessments and Surveys (Baseline) • Week 1 (following Visit 2) – Gameplay – daily transmission of game data • Week 1 – Survey – data transmission • Visit 3 – Assessments and Surveys • Week 2 – Gameplay – daily transmission of game data • Week 2 – Survey – data transmission • Visit 4 – Assessments and Surveys • Week 3 – Gameplay – daily transmission of game data • Week 3 – Survey – data transmission • Visit 5 – Assessments and Surveys • Week 4 – Gameplay – daily transmission of game data • Week 4 – Survey – data transmission • Visit 6 – Assessments and Surveys 
(Note: Phase II may not begin immediately following phase I)
 
Phase II
 
 • Week 1 – Gameplay – daily transmission of game data • Week 1 – Survey – data transmission • Visit 1 – Assessments and Surveys |

| | |
|--------------------------------------|--|
| | 
 • Week 2 – Gameplay – daily transmission of game data • Week 2 – Survey – data transmission • Visit 2 – Assessments and Surveys • Week 3 – Gameplay – daily transmission of game data • Week 3 – Survey – data transmission • Visit 3 – Assessments and Surveys • Week 4 – Gameplay– daily transmission of game data • Week 4 – Survey – data transmission • Visit 4 – Assessments and Surveys |
| Efficacy Evaluations | 
The primary efficacy endpoints will be:
 
The mean change from baseline score on the following assessments based on post-final game play session assessment compared to the alternate game group:
 
 a. Subject gaze patterns as measured by video eye tracking assessment. b. Subject gaze patterns as measured by the dyadic interaction task. c. Mean change in baseline score on the Ekman 60 Faces Test. d. Mean change in baseline score on the TOVA. e. Mean change in baseline score on the SRS. 
Secondary endpoints:
 
The mean change from baseline score on the following assessments based on post-final game play session assessment compared to the alternate game group:
 
 a. Subject gaze patterns as measured on the videos of emotional expression assessment. b. Subject responses to the CJARS survey. |
| Pharmacokinetic Evaluations | N/A |
| Safety Evaluations | 
Subjects will always be supervised by a parent, teacher, or therapist (therapist includes Registered Behavior Technicians, assistant speech pathologists, assistant behavior analysts (BCABA), and teaching assistants) during use of the BioStream training and alternative game. Clinical adverse events (AEs) will be monitored throughout the study through parent reporting in the case of at home use and through teacher reporting in the case of in school use. Since the study procedures are not greater than minimal risk, AEs are not expected.
 |
| Statistical And Analytic Plan | 
Paired-sample t-tests will be used to measure changes from baseline within each group, and independent sample t-tests will be used to measure changes from baseline relative to the alternate game group for all endpoints.
 |

For all endpoints, we will determine whether there were observable changes in scores from baseline or relative to the alternate game group and whether these changes are statistically significant. Significance will be set at $p < 0.05$. Multiplicity of primary endpoints will be managed via statistical corrections.

**DATA AND SAFETY
MONITORING PLAN**

The PI will periodically review the data collection and storage practices associated with this study and determine whether changes to enhance confidentiality and privacy are required. The PI will frequently monitor the quality control of the data with staff and research assistants.

All written or electronic forms (except Informed Consent Forms and Assent Forms) will employ a unique alphanumeric identifier; in no case will the participant's name or other identifying information appear on these forms. The user ID for the BioStream Training and alternate game shall use the same unique alphanumeric identifier. The study team will accomplish this on all parent/guardian or teacher or therapist questionnaires (as applicable) which have lines for child and parent name by applying a label with unique alphanumeric identifier and instructing parents/guardians or teacher or therapists to use generic labels (e.g., biological mother) rather than writing their names. The PI will keep a master list containing PHI and subject ID number separate from coded data forms, which will be maintained in a locked file drawer, cabinet, or lock box in the PI's office. Only the PI will have access to this location. The master list will be maintained on a separate password-protected computer and be stored in an encrypted password protected file. Video recordings will stored on password-protected and/or encrypted data storage devices including computers, external hard drives, and/or flash drives only accessible by members of the study team.

**TABLE 1: SCHEDULE OF STUDY PROCEDURES
(INITIAL SCREENING)**

| | Estimated time | Parent or subject? |
|---|-----------------------|---------------------------|
| Informed Consent | 15 minutes | Parent |
| Review of Inclusion/Exclusion Criteria (Initial Screening Interview) | 15 minutes | Parent |
| Video Game Interview Form (Parent-Report) | 15 minutes | Parent |

**TABLE 2: PHASE I SCHEDULE OF STUDY PROCEDURES
(HOME, SCHOOL, THERAPY CENTER, OR RESEARCH ORGANIZATION)**

| | Estimated time (total over all visits) | Parent or subject? | Visits applicable (Total 6 Visits) |
|--|---|---------------------------|---|
| Informed Consent/Assent (if applicable) | 30 minutes | Parent and subject | Visit 1 |

| | | | |
|---|----------------------------------|----------------|--|
| Peabody Picture Vocabulary Test (PPVT) | 20 minutes | Subject | Visit 1 |
| Ekman 60 Faces Test | 10 minutes | Subject | Visit 1 |
| SRS (Parent-Report) | 50 minutes | Parent | Visits 2-6 |
| C-JARS (Parent-Report) | 50 minutes | Parent | Visits 2-6 |
| Dyadic Interaction Task | 50 minutes | Subject | Visits 2-6 |
| Eye Tracking Video Assessment | 50 minutes | Subject | Visits 2-6 |
| Ekman 60 Faces Test | 50 minutes | Subject | Visits 2-6 |
| Emotional Expression Video Assessment | 50 minutes | Subject | Visits 2-6 |
| TOVA | 109 minutes | Subject | Visits 2-6 |
| Game and equipment introduction (if applicable) | 40-60 minutes | Parent | Visit 1 |
| BioStream Training | 6.67-33.33 hours | Subject | Over a period of 28 days following Visit 2 |
| Weekly Parental/Teacher/Therapist Survey | 20 minutes | Parent | 1 survey/per week |
| Subject Interview/Survey (if applicable) | 40 minutes | Subject | Visits 3 - 6 |
| Parent/Teacher/Therapist Interview/Survey (if applicable) | 40 minutes | Parent | Visits 3 - 6 |
| Equipment return (if applicable) | 5 minutes | Parent | Visit 6 |
| TOTAL | 13.48 hours – 41.15 hours | Subject | |
| TOTAL | ~4.25 hours* | Parent | *Excludes time spent for oversight of subject during BioStream Training |

**TABLE 3: PHASE II SCHEDULE OF STUDY PROCEDURES
(HOME, SCHOOL, THERAPY CENTER, OR RESEARCH ORGANIZATION)**

| | Estimated time (total over all visits) | Parent or subject? | Visits applicable (Total 4 Visits) |
|---------------------------------------|---|---------------------------|---|
| SRS (Parent-Report) | 40 minutes | Parent | All Visits |
| C-JARS (Parent-Report) | 40 minutes | Parent | All Visits |
| Dyadic Interaction Task | 40 minutes | Subject | All Visits |
| Eye Tracking Video Assessment | 40 minutes | Subject | All Visits |
| Ekman 60 Faces Test | 40 minutes | Subject | All Visits |
| Emotional Expression Video Assessment | 40 minutes | Subject | All Visits |
| TOVA | 87 minutes | Subject | All Visits |
| BioStream Training | 6.67-33.33 hours | Subject | Over a period of 28 |

| | | | |
|---|----------------------------------|----------------|--|
| | | | days |
| Weekly Parental/Teacher/Therapist Survey | 20 minutes | Parent | 1 survey/per week |
| Subject Interview/Survey (if applicable) | 40 minutes | Subject | All Visits |
| Parent/Teacher/Therapist Interview/Survey (if applicable) | 40 minutes | Parent | All Visits |
| Equipment return (if applicable). | 5 minutes | Parent | Visit 4 |
| TOTAL | 11.45 hours – 38.12 hours | Subject | |
| TOTAL | ~2.5 hours* | Parent | *Excludes time spent for oversight of subject during BioStream Training |

1 BACKGROUND INFORMATION AND RATIONALE

1.1 Introduction

Autism spectrum disorder (ASD) is a neurodevelopmental disorder characterized in part by difficulty in social interaction and communication [1], which can affect individuals' employability, educational achievement, and quality of interpersonal relationships [2-4]. Existing therapies targeting the deficits of the school-age population with ASD require significant therapist or educator time and are thus very costly. Given this, as well as the fact that ASD affects 1 in 59 children in the United States according to the Center for Disease Control, there is a pressing need for cost-effective, evidence-based interventions to support the ASD community.

BioStream Technologies, LLC (BioStream), in collaboration with the Center for Autism Research (CAR) at the Children's Hospital of Philadelphia (CHOP), has developed one such intervention: the BioStream Computer-Based Social Skills Training (BioStream Training). The intervention to be used in this protocol has been piloted at CHOP as part of an existing IRB protocol (eIRB #15-12594). As part of that protocol, we have run 32 children (18 with ASD and 14 TDC) through procedures that to some degree are overlapping with the present protocol (up to 5 study sessions of gameplay per subject).

The primary objective of this study is to evaluate changes in subject performance on social skills assessments after engaging in BioStream Training, including in comparison to an alternate game. The secondary objective of this study is to evaluate changes in subject gaze patterns during social skills assessments after engaging in BioStream Training, including in comparison to an alternate game and to evaluate possible correlations in changes in social skills assessments with changes in subject gameplay performance.

Subject computer gameplay data (including game performance, game usage, and eye tracking data), certain subject assessment data, and certain subject survey data, may be

collected and stored using a laptop computer with integrated use of a consumer grade eye tracker connected to it via a USB wired connection (Subject Computer). **All data collected and stored on the Subject Computer will be de-identified data.**

Certain subject assessment and survey data may also be collected manually using a handwritten paper-based data collection method and stored digitally through use of digital scanning.

Additionally, subject eye contact video recording data may also be collected using a video camera and/or video camera embedded glasses worn by any member of the study team during real world dyadic interaction task assessment. **This data will not be stored on or collected using the Subject Computer. This data will be stored on a separate computer and/or computer data storage device maintained by any member of the study team. This data may also be sent to HIPAA compliant third parties including therapist practitioners or research organizations. These HIPAA compliant third parties, blinded to the study group of each subject, will be used to annotate the video recordings of the dyadic interaction task assessments including for subject eye contact during the task.**

Certain Parent assessment and survey data may be collected using a computer (**excluding the Subject Computer except in the case of the Weekly Parental/Teacher/Therapist Survey**) and/or manually using handwritten paper-based data collection methods. The parent or teacher or therapist (as applicable) may complete a Weekly Parental/Teacher/Therapist Survey using a form on the Subject Computer. **This survey is configured so that only de-identified data may be included in the survey or associated with the survey.**

1.2 Name and Description of Investigational Product or Intervention

The study intervention is the BioStream Computer-Based Social Skills Training (BioStream Training). BioStream Training is computer-based social skills training that includes interactive game-like applications involving images (e.g. photos and/or videos of people making different emotional expressions), animation (e.g. animated characters), video (e.g. tutorials), and audio (e.g. sound effects). Subjects can interact with portions of BioStream Training using an eye tracker (i.e. by using their gaze as a real-time input to the game-like applications).

Computer tasks will involve presenting various stimulus types to the participant. These will include action sequences, designed to be very engaging, and social sequences, designed to task users with social skills exercises.

Audiovisual stimuli: The social stimuli will include photographs and videos as well as animated characters. Animated social stimuli will include various characters that may interact with the user, may present the user with tasks, and may guide the user in tasks. Characters may socially interact with the user by eye contact, facial expression, body language, and speech.

The non-social stimuli will include computer graphics of various environments in which the user will navigate and interact in different ways including collection of items that the user may use in the game-like application segment. Parents/guardians will be given the

opportunity to see examples of the pictures and graphics that will be shown to their child as part of the consent process.

Computer interaction sessions will take place in the home and/or school environment. Subjects will sit facing a computer, tablet, or smartphone screen and be positioned so that the eye tracking device can obtain measurements. Subjects may be provided headphones to wear during the computer interaction to enable audio listening without disturbing others in the home, school, therapy center, or research organization environment. Subjects may be provided with a computer mouse, computer keyboard, touchscreen, and/or game controller device. Subjects may be presented with multiple action and social sequences. Perspectives in the computer application may include first-person and third-person views. An eye tracker will record participants' gaze patterns. Participants' use of the controls in the game-like application—computer mouse, computer keyboard, touchscreen, and/or game controller device—will be recorded. All measurements will be taken in real time and may affect the stimuli presented.

Action Sequences: Subjects will view and navigate animated environments on the screen. Action sequences may include items that can be obtained and used for special abilities in the game environment. Subjects may be instructed to use the controls for abilities including turn, run, jump, obtain item, and use item. Any or all behavioral measures will be used to determine engagement, including game performance data and attention from eye gaze data.

Social Sequences: Subjects will be presented with social tasks in the context of gameplay which may include normative eye contact, facial emotion recognition, joint attention exercises, perspective taking exercises, vocal emotion recognition, and normative internal and external emotional response in social interactions. Social sequences may include simulated interaction with social stimuli presenting different personality traits such as extraversion, caution, and aggression. Social sequences may vary and change based on real-time behavioral measurements (including eye tracking measurements/data) and may include the following examples. Subjects may be encouraged to use appropriate eye contact with social stimuli; eye contact will be measured with the eye tracker. Subjects may be prompted to identify the emotion presented by social stimuli based on facial expression. Subjects may be prompted to identify the emotion presented by social stimuli based on vocal expression. Subjects may be instructed to use the controls including the game controller to choose responses in recognition tasks. General emotions to recognize may include pleasantness, unpleasantness, and neutrality. Specific emotions to recognize may include happiness, surprise, sadness, anger, fear, and disgust.

Data Transfer and Storage: Subject computer gameplay data (including game performance, game usage, and eye tracking data), certain subject assessment data, and certain subject survey data, may be collected and stored using a laptop computer with integrated use of a consumer grade eye tracker connected to it via a USB wired connection (Subject Computer). Additionally, the parent, teacher, or therapist (as applicable) may complete a Weekly Parental/Teacher/Therapist Survey using a form on the Subject Computer. This survey is configured so that only de-identified data may be included in the survey or associated with the survey. **All data collected and stored on the Subject Computer will be de-identified data.**

De-identified study data collected and stored on the Subject Computer may at any time be copied (including for backup purposes or remote data analysis purposes) to a computer data storage device (including a USB flash drive or external computer hard drive) or to a separate computer, by any member of the study team by establishing a wired connection between the computer data storage device or separate computer and the Subject Computer (or direct connection in the case of a USB Flash Drive) to manually copy the de-identified study data from the Subject Computer to such device or computer. This data may at any time be transferred by any member of the study team to the Sponsor including for backup and analysis purposes to ensure data integrity.

Additionally, the Subject Computer may be configured to manually enable transmission and/or automatically and regularly provide for transmission, of de-identified study data to the Sponsor's computer (including for backup and analysis purposes) using a wireless communication link (which may include use the parent/guardian home's, the school's, the therapy center's or the research organizations, as applicable, Wi-Fi internet connection) between the Subject Computer and the Sponsor's computer. **No subject's internet protocol address (IP Address) will be collected or stored by the Sponsor at any time including as a result of this communication link.** This de-identified study data may be retransmitted to any member of the study team electronically or via access to a password protected web interface, for backup purposes, analysis purposes, study monitoring purposes (including in the case of the Weekly Parental/Teacher/Therapist Survey), or for use in determining the necessity of teacher, therapist, parent and/or subject follow up to prompt subject compliance with the study protocol.

Sponsor may provide a web interface for password protected access by any or select members of the study team that shows and/or permits the download of, subject de-identified study data using secure channels which may include secure FTP or HTTPS. The Sponsor may electronically send to any member of the study team reports containing subject de-identified study data. The Sponsor may otherwise electronically communicate subject de-identified study data to any member of the study team. The communication of this de-identified study data to any member of the study team will facilitate monitoring for compliance and data integrity in a real-time fashion.

Sponsor may notify any member of the study team about any subject ID numbers that failed to play the intervention or the alternate game over any 24-hour period. Any member of the study team may reach out to subjects and/or parents and teachers or therapists (as applicable) to remind them to play (by phone, email, and/or text message). Subjects will also have the opportunity to contact any or select members of the study team through phone or email if any questions arise.

The Sponsor may, from time to time, transmit updates to the software installed on the Subject Computer using the communication link described above.

Alternate Comparison Game:

The BioStream Training is being compared to a modified version of the BioStream Training, which will not include the same therapeutic exercises. The game will be played by subjects in the non-intervention group for the same length of playing time and at the same frequency,

as the BioStream Training intervention group. It will require a similar game controller device as that which is used by the intervention group and will be computer based. The Sponsor may also use as the alternate comparison game any video game that is rated E (Everyone) by the Entertainment Software Rating Board.

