3 INVESTIGATIONAL PLAN

3.1 General Schema of Study Design

This protocol is a comparison group controlled trial of a computer-based social skills training intervention. The BioStream Training is being compared to a modified version of the BioStream Training, which will not include the same therapeutic exercises or any video game that is rated E (Everyone) by the Entertainment Software Rating Board. The game will be played by subjects in the non-intervention group for the same length of playing time and at the same frequency, as the BioStream Training intervention group. It will require a similar game controller device as that which is used by the intervention group and will be computer based.

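### The control may be a modified BioStream game or any E-rated video game, with no rule for choosing, yet the analysis treats all controls as one group

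*Combined protocol and SAP*

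**What the plan says.** Section 1.2 of the protocol, under the alternate comparison game, starts with one comparator: "The BioStream Training is being compared to a modified version of the BioStream Training, which will not include the same therapeutic exercises". The same passage ends with a second: "The Sponsor may also use as the alternate comparison game any video game that is rated E (Everyone) by the Entertainment Software Rating Board".

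Section 3.1 puts the two options into one sentence: "which will not include the same therapeutic exercises or any video game that is rated E (Everyone) by the Entertainment Software Rating Board". The syntax is awkward, but section 1.2 makes clear that the E-rated game is an alternative control. Section 3.1 then requires the control game to be played "for the same length of playing time and at the same frequency" as the training, and adds: "It will require a similar game controller device as that which is used by the intervention group and will be computer based".

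Sections 3.2 and 7.1.1 randomise to two groups, BioStream Training or alternate game. Sections 5.5 and 5.7.2 compare change from baseline with the alternate game group by independent-sample t-test. The Supplement to the Statistical Analysis Plan adds a mixed ANOVA with a two-level Condition factor. None of these separates the controls by the game they played.

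**The concern.** A between-arm difference has meaning only in relation to a stated comparator. Here there are two possible ones, and they may differ a good deal. The modified version is built from the product under test. An E-rated title need share nothing with it beyond playing time, frequency, controller type and computer format. The training itself includes more than social exercises: "These will include action sequences, designed to be very engaging, and social sequences, designed to task users with social skills exercises". A commercial game may be more or less engaging than those action sequences.

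The text gives the sponsor the choice without stating how it is made, whether all controls must get the same game, or whether the game played is recorded for analysis. With 10 sites (section 3.3.2) and two phases, the mix could vary by site or phase without breaching the protocol. The estimate would then depend on that mix as well as on the training, and the planned analyses could not separate the two.

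**Working it through.** **What fixes the comparator**

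| Question | Where it would be settled | What is there |
|---|---|---|
| Which game is the control? | 1.2, 3.1 | Two options, no rule for choosing |
| Same game for every control child? | 1.2, 3.1, 3.1.4 | Not stated |
| Choice tied to site, phase or date? | 1.2, 1.3, 3.1, 3.3 | Not stated |
| What is matched between arms? | 3.1 | Time, frequency, similar controller, computer based |
| Is the control group split in randomisation? | 3.2, 7.1.1 | No, one alternate game group |
| Is it split in the analysis? | 5.5, 5.7.2, SAP supplement | No, controls pooled |

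The permission to use either game is explicit, and no later section narrows it.

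**What the pooled test estimates**

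Let d be the mean effect of BioStream Training against the modified game, q the share of controls who play an E-rated game, and g the additional difference when the control is an E-rated game. Then

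expected contrast = d + q × g.

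The plan states neither q nor g, and g can have either sign. If d = 0.30 SD and q = 0.5, the contrast is 0.30 + 0.5 × 0.2 = 0.40 SD for g = +0.2, and 0.30 − 0.5 × 0.2 = 0.20 SD for g = −0.2. At q = 1 the two values are 0.50 and 0.10 SD.

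**Illustrative size**

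The plan gives no figure to reproduce: section 5.8 states up to 150 participants, with no effect size, SD, power or dropout. The assumptions are 75 per arm (150 split 1:1, no dropout), equal SD at baseline and final visit, baseline-to-final correlation r of 0.5 or 0.7, two-sided 0.05 without correction, and a normal approximation. Shifts are in SDs of the score.

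- SE of the difference in mean change = √[2(1 − r) × 2/75].
- r = 0.5: √(1.0 × 2/75) = 0.163 SD.
- r = 0.7: √(0.6 × 2/75) = 0.126 SD.
- Chance of a significant result when d = 0 and the shift is b = q × g: Φ(|b|/SE − 1.96) + Φ(−|b|/SE − 1.96).

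| Shift b (either sign) | r = 0.5 | r = 0.7 |
|---|---|---|
| 0 | 5.0% | 5.0% |
| 0.1 SD (e.g. q = 0.5, g = 0.2) | 9.4% | 12.4% |
| 0.2 SD (e.g. q = 1, g = 0.2) | 23.2% | 35.3% |

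Sections 5.5 and 5.7.2 promise a correction across the primary endpoints but do not name it. If it were Bonferroni over the five listed (alpha 0.01, critical value 2.576), the 0.1 SD row becomes 2.6% and 3.8% and the 0.2 SD row 8.8% and 16.0%, against 1% with no shift.

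These are chances of significance in either direction. With b negative, nearly all of them favour the control, and a real benefit of the training would be partly hidden.

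**The case against.** The strongest reply is that section 2.1 asks only whether BioStream Training improves scores compared with an alternate game. That is a comparison of whole games, so a real difference from a commercial title is not a false positive for the stated aim. This stands: the plan cannot be faulted for failing an aim it does not set. It does not answer the blending problem, because a comparison of whole games still needs to say which game.

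Section 3.1 also matches time, frequency, controller and format for both options, so the control is far from unmatched. The wording in section 1.2 is compatible with one choice made once. A reader might infer that games were swapped during the trial, or that both kinds were used. The documents show neither; they only leave both open.

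Two stronger readings are tempting and should not be adopted.

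- **Eye-tracker familiarity.** Section 1.2 says "Subjects can interact with portions of BioStream Training using an eye tracker", so a reader might infer that an E-rated control makes the arms differ in familiarity with the device used for the gaze endpoints. But section 5.4.2 lists an eye tracker among the equipment supplied for either game, and both arms take the same eye-tracking assessments. Nothing says that the modified version uses gaze as input, so that option is not shown to avoid the problem.
- **Parent unmasking.** A commercial title might reveal the arm to the parent who completes the SRS and C-JARS. But the plan describes no blinding of parents under either control. They can see example stimuli at consent, and in home use they are trained on the assigned game. This is a separate matter that the choice of control does not settle.

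**Conclusion.** The concern holds in a limited form. The plan expressly permits two kinds of control, sets no rule for choosing between them, and pools them in randomisation and analysis. If both are used, the between-arm estimate is a blend whose mix depends on the sponsor's choice. If only one is used throughout, there is no blend, but the plan does not say which contrast is being estimated.

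The direction of the shift is unknown and its size cannot be derived from the documents. The illustrative range of about 9% to 35% rests entirely on the assumed shift, correlation, allocation and full enrolment, and falls under a multiplicity correction. It shows that a modest shift could matter at this sample size, not that one occurred.

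A reader might infer that requiring the modified version would isolate the effect of the social exercises. The documents do not support that either: leaving out the same exercises is not the same as having none, and the plan does not say that the two versions are otherwise identical.

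**What to change.** In sections 1.2 and 3.1, delete the E-rated option so that every control child plays the modified version already named as the comparator. If the sponsor needs a different game, name one single game for all control children, at all sites and in both phases, before the first randomisation.

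Under either choice:

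- record for each child which game was played;
- describe the result as BioStream Training versus that named game, and claim the isolated effect of the exercises only if the protocol states that the modified version differs in the exercises alone.

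The cost is a wording change in two sections and one recorded item per child. The sponsor gives up the freedom to choose or change the control game.
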